There are no major overlapping toxicities relating to valproic acid, sorafenib, or sildenafil that suggest that the combination would be subject to higher rates of toxicity. There is a low incidence of diarrhea in patients treated with sorafenib that may be exacerbated with valproic acid; this will be monitored closely. There is an early stopping rule in place should there be unexpected significant toxicities from the combination. It is expected from clinical experience that a fraction of patients will not tolerate full dose sorafenib in the chronic setting, and these patients may continue therapy at reduced dose levels.

One previously published study has evaluated sorafenib in combination with sildenafil (32). This study was a non-cancer study, which treated patients with pulmonary hypertension with sorafenib and prostanoid therapy, half of whom were also on chronic sildenafil. No grade 3 or 4 drug-related toxicities were reported.

Children under the age of 18 will be excluded from study. There are no published reports regarding the safety of sorafenib at the fixed dose of 400 mg orally, twice a day, in the pediatric population, and evaluating the safety of full dose sorafenib in the pediatric population is beyond the scope of the study.

In patients with progressive high-grade glioma, survival time is generally short. Six-month PFS will be used as the primary endpoint in the study. This endpoint has been accepted by the FDA as a reasonable endpoint in recurrent or progressive GBM, and a positive 6-month PFS led to the approval of bevacizumab as second-line therapy in this disease.

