- 4.2.13 Arterial thromboembolic or embolic events such as myocardial infarction, cerebrovascular accident, including transient ischemic attacks within 6 months prior to first study treatment.
- 4.2.14 Serious uncontrolled infection > grade 2 (CTCAE v4.0).
- 4.2.15 Known HIV positivity.
- 4.2.16 Unable to swallow medication or suspected malabsorption.
- 4.2.17 Patients on chronic nitrate therapy or alpha-blockers.
- 4.2.18 Exclude persons who require ongoing administration of STRONG CYP3A4 inhibitors and/or STRONG CYP3A4 inducers and/or STRONG CYP2C9 inhibitors. Examples of clinical inhibitors and clinical inducers for P450-mediated metabolisms and classification of strong, moderate, and weak interactions are available through the FDA website, Table 3-2 and 3-3:
<http://www.fda.gov/Drugs/DevelopmentApprovalProcess/DevelopmentResources/DrugInteractionsLabeling/ucm093664.htm>
- 4.2.19 Women who are pregnant or nursing.
- 4.2.20 Persistent heart rate (HR) < 50 or > 120 beats per minute (bpm).
- 4.2.21 QTc > 480 ms (grade 2 or greater) on screening ECG*.

* If baseline QTc on screening ECG meets exclusion criteria on screening assessment:

- Check potassium and magnesium levels
- Correct any identified hypokalemia and/or hypomagnesemia and repeat ECG to confirm exclusion of patient due to QTc
- For patients with a HR 60-100 bpm, no manual read of QT is required.
- For patients with baseline HR < 60 or > 100 bpm, manual read of QT by cardiologist is required using Fridericia correction.

4.2.22 Other condition(s) that in the opinion of the investigator might compromise the objectives of the study.

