6.4.2 Qualifying Toxicities for the Safety Lead-In and Safety Stopping Rule

Qualifying toxicities for the safety lead-in are evaluated weekly during the first 4 weeks of combination treatment for each of the first 6 patients deemed evaluable for qualifying toxicity for the safety lead-in (see Section [10.1](#)).

Qualifying toxicities for the safety stopping rule are evaluated regularly during the first 4-week cycle of combination treatment for patients deemed evaluable for the early stopping rule (see Section [10.1](#)).

Qualifying toxicities are defined as any of the following that are possibly, probably, or definitely related to drug therapy:

Any grade \geq 3 toxicity, except the following:

- nausea, vomiting, or diarrhea in the absence of adequate prophylaxis and/or responsive to medical management
- grade 3 thromboembolic event

- grade 3 hyperglycemia
- grade 3 PPE (hand-foot syndrome)
- fatigue responsive to medical management
- grade 3 hypertension
- electrolyte abnormalities that, once corrected, can be maintained with oral repletion
- grade 3 anemia, platelets, neutrophils, WBC, lymphocytes, febrile neutropenia

6.4.3 See Section [8.5](#) for AE and qualifying toxicity reporting procedures.

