Any grade 2 non-hematologic toxicity that is persistent, intolerable, or unresponsive to optimal management	At the treating investigator's discretion, consider holding or continuing treatment at 1 dose reduction.
Grade 3	
1st occurrence:
 
 • Hold sorafenib until resolution to ≤ grade 2 or baseline. • When resuming sorafenib, decrease the sorafenib dose by one dose reduction. • If toxicity persists >14 days of treatment delay, discontinue sorafenib. 
No improvement within 7 days; or 2nd or 3rd occurrence:
 
 • Hold sorafenib until resolution to ≤ grade 2 or baseline. • When resuming sorafenib, decrease the sorafenib dose by 2 dose reductions. • If toxicity persists >14 days of treatment delay, discontinue sorafenib 
4th occurrence:
 
 • Hold sorafenib until resolution to ≤ grade 2 or baseline. • When resuming sorafenib, decrease the sorafenib dose by 3 dose reductions. • If toxicity persists >14 days of treatment delay, discontinue sorafenib
Grade 4	Discontinue sorafenib permanently.

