7.4 General Concomitant Medication and Supportive Care Guidelines

(see also Section [9](#))

- 7.4.1 Fluids should be administered as indicated to prevent/treat dehydration. Maintain appropriate electrolyte balance including correction of hypokalemia and hypomagnesemia, and hypophosphatemia, if possible, prior to and during study treatment. In those patients who demonstrate electrolyte abnormalities, oral supplementation should be considered as a standard supportive measure to keep magnesium levels at \geq LLN for the laboratory, potassium levels at \geq LLN for the laboratory, and phosphorus levels at or above 2.4 mg/dL.
- 7.4.2 Clinically significant diarrhea should be managed aggressively to prevent electrolyte abnormalities and dehydration.
- 7.4.3 Concurrent administration of other anti-neoplastic agents with the study combination regimen is prohibited.
- 7.4.4 Concurrent administration of organic nitrates or alpha-blockers with the study combination regimen is prohibited.
- 7.4.5 Cautionary statements about other concurrent medications:

Addition of any STRONG CYP inhibitors and/or inducers per examples on the FDA website

(<http://www.fda.gov/Drugs/DevelopmentApprovalProcess/DevelopmentResources/DrugInteractionsLabeling/ucm093664.htm>) during study participation should prompt treating investigator awareness of possible interactions. Specifically:

- Caution should be observed if sorafenib is to be coadministered with CYP3A4 inducers such as rifampin, rifampicin, St. John's wort, phenytoin, carbamazepine, phenobarbital, and dexamethasone (for reference see <http://www.fda.gov/Drugs/DevelopmentApprovalProcess/DevelopmentResources/DrugInteractionsLabeling/ucm093664.htm>) may increase metabolism of sorafenib, decreasing sorafenib plasma concentrations
- Caution should be observed if sildenafil is to be coadministered with CYP3A4 or CYP2C9 inhibitors (for reference see <http://www.fda.gov/Drugs/DevelopmentApprovalProcess/DevelopmentResources/DrugInteractionsLabeling/ucm093664.htm>)

- 7.4.6 Caution should be observed if valproic acid is to be coadministered with any of the following: aspirin, carbapenem antibiotics (ertapenem, imipenem, meropenem), rifampin.

- 7.4.7 PPE (hand-foot syndrome)

Biopsy specimens of patients with PPE secondary to tyrosine kinase inhibition show hyperkeratosis, keratinocyte necrosis, and dermal inflammation. Recommended management strategies for skin toxicities consistent with PPE are summarized in the following sections:

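### The gastrointestinal exception in Section 6.4.2 joins its two conditions with and/or and has no grade limit, so grade 4 or refractory diarrhea can stay out of the lead-in and stopping-rule counts

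*Combined protocol and SAP*

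**What the plan says.** Section 6.4.2 defines a qualifying toxicity as any possibly, probably or definitely drug-related event of grade 3 or higher, less eight exceptions. The first is "nausea, vomiting, or diarrhea in the absence of adequate prophylaxis and/or responsive to medical management". Five others carry a grade limit, for example "grade 3 hyperglycemia" and "grade 3 thromboembolic event"; hand-foot syndrome, hypertension and the blood-count bullet are limited in the same way. The gastrointestinal, fatigue and electrolyte bullets have no limit. Fatigue and electrolytes each rest on one condition; only the gastrointestinal bullet joins two with and/or.

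The definition feeds two rules. The lead-in (13.6.1) allows expansion if fewer than 2 of 6 evaluable patients have a qualifying toxicity in the first 4 weeks. The sequential rule (13.6.2) stops accrual for DSMC review when m of n patients reaches a listed boundary, from 5/7 to 32/66.

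On diarrhea itself, Section 1.7 says: "There is a low incidence of diarrhea in patients treated with sorafenib that may be exacerbated with valproic acid; this will be monitored closely". Section 7.4.2 says: "Clinically significant diarrhea should be managed aggressively to prevent electrolyte abnormalities and dehydration". For grade 4 events under other non-hematologic toxicities, Table 1 says: "Discontinue sorafenib permanently". Section 10.1 makes a lead-in patient evaluable only with twice-daily sorafenib on at least 21 of the first 28 days, or with a qualifying toxicity; other lead-in patients are replaced.

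**The concern.** With and/or, meeting either condition exempts the event. An event that does not respond to treatment is then exempt because of something that happened before it, namely that prophylaxis was not adequate. With no grade limit, the exemption extends to grades 4 and 5. The readable text does not define adequate prophylaxis, so two assessors could classify the same event differently.

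This matters more for diarrhea than for most toxicities. It is the event Section 1.7 singles out as possibly worsened by the combination, and Section 13.1 presents the lead-in as protection against interaction toxicity. Two events in six patients decide expansion, so classifying one event can change the result.

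Section 10.1 adds to the problem. Suppose exempt grade 4 diarrhea leads to sorafenib being stopped before 21 days of dosing. The patient has no qualifying toxicity and too little exposure, so is non-evaluable and replaced. A severe early case then leaves both the numerator and the denominator of the lead-in.

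**Working it through.** **1. The literal logic.** Let P mean adequate prophylaxis was given and R mean the event responded. The exception applies if (not P) or R.

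| Grade 3 or higher GI event | R | not R |
|---|---|---|
| not P | exempt | exempt |
| P | exempt | counts |

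Grade does not enter. A fatal event cannot have responded, so it is exempt only through the not-P row. On a strict *and* reading (not P and R), every refractory event counts. The text does not say which reading applies.

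**2. The plan's own figures.** The boundaries reproduce as the smallest m whose 95% Wald lower limit, m/n − 1.96·√[(m/n)(1 − m/n)/n], exceeds 0.35.
- n = 7: 5/7 gives 0.380 and 4/7 gives 0.205.
- n = 66: 32/66 gives 0.364 and 31/66 gives 0.349.
- All 60 values from n = 7 to 66 agree.

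The boundary arithmetic is sound. The issue is which events enter m.

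**3. Effect on the lead-in.** The rule is taken as a pass with fewer than 2 of 6 qualifying toxicities, as in 13.1, 13.6.3 and the later sentences of 13.6.1 (one sentence of 13.6.1 has it the other way round).

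Inputs:
- q = 10%, other qualifying toxicity (assumed; the documents give no figure).
- d = rate of grade 3 or higher diarrhea. Section 1.7 cites grade 3 diarrhea of 1/6 (17%) and 1/19 (5%) in the two parts of the temsirolimus study, 2% in the erlotinib study, and 1 patient (2%) of 43 at grade 3–4 in one temozolomide study.
- s = share of that diarrhea that clearer wording would newly count (assumed 25–50%). The rest is taken to stay exempt.
- Diarrhea and other toxicity are taken as independent.

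Formulas: p = 1 − (1 − q)(1 − s·d); P(pass) = (1 − p)⁶ + 6p(1 − p)⁵.

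With diarrhea exempt, p = 0.10 and P(pass) = 0.531 + 0.354 = 0.886.

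| d | p, s = 25% | P(pass) | p, s = 50% | P(pass) |
|---|---|---|---|---|
| 2% | 0.1045 | 0.88 | 0.1090 | 0.87 |
| 5% | 0.1113 | 0.86 | 0.1225 | 0.84 |
| 17% | 0.1383 | 0.80 | 0.1765 | 0.71 |

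Worked case, d = 17% and s = 50%: s·d = 0.085; p = 1 − 0.9 × 0.915 = 0.1765; P(pass) = 0.312 + 0.401 = 0.713.

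As a ceiling, counting all diarrhea (s = 100%) gives 0.79 at 5% and 0.53 at 17%. That is more than the fix would do, because some responsive grade 3 events would remain exempt.

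**4. Effect on the sequential rule.** An exact recursion over the stated boundaries, ignoring the lead-in, gives the chance of crossing by n = 33 as below 0.001 at p = 0.10, 0.002 at 0.15 and 0.007 at 0.20. At these rates the boundaries are almost never reached under either definition, so the practical effect falls on the lead-in.

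**The case against.** **Not all diarrhea is excluded.** A reader might infer that no diarrhea event can ever count. That needs the most permissive reading and a finding of inadequate prophylaxis in every patient. Section 7.4 refers to Section 9, which is redacted and may contain such guidance, so its absence from the readable text cannot be held against the plan. Diarrhea refractory despite adequate prophylaxis counts on any reading.

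**Larger numbers.** A reader might assume 30% diarrhea, all of it counted, and reach a pass probability of 0.28. That rate is above every rate the protocol cites, and clearer wording would still exempt some of those events.

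**Infarction.** Section 4.2.13 lists "Arterial thromboembolic or embolic events such as myocardial infarction, cerebrovascular accident", so a reader might infer that grade 3 infarction is exempt as a thromboembolic event. The documents do not support this. Events are graded by CTCAE term, and Table 1 lists myocardial infarction as its own graded entry. An eligibility criterion does not define event coding. Only a clarification is warranted.

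**Table 1.** Stopping sorafenib was never the counting criterion: Table 1 also stops it for some grade 2 events, which cannot qualify. This stands. The mismatch is not a contradiction by itself, but combined with the Section 10.1 replacement rule it affects who is counted.

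**Other safeguards.** Related dehydration of grade 3 or higher is not exempt. Adverse events and SAEs are recorded, and unanticipated problems go to the DSMC. Section 1.7 also denies major overlapping toxicities. These points reduce the risk of missing harm, but none of these reporting routes feeds the lead-in or m/n counts. Table 5 gives the DSMC expedited notice only of unanticipated problems and qualifying toxicities, so an exempt diarrhea SAE that is neither would not take that route.

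**Conclusion.** The concern holds as a fault in the counting rule. Followed as written, Section 6.4.2 can leave grade 4, refractory or fatal diarrhea out of both safety rules, and Section 10.1 can remove the patient from the lead-in as well.

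The size is moderate: a fall in the lead-in pass probability from 0.89 of about 0.02–0.05 at the cited 5% rate and about 0.08–0.17 at the cited 17%. These figures rest on the assumed 10% background rate, the assumed 25–50% share and independence. The cited rates are themselves weak inputs: the 17% is one patient in six, and the documents do not say that they are first-cycle rates. The effect would be larger only if the combination raised diarrhea above the cited rates, which is the possibility Section 1.7 raises.

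**What to change.** Amend Section 6.4.2, changing only what is counted:

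- Replace and/or with explicit logic, so that an event that does not respond to management is not exempt merely because prophylaxis was lacking. Say what adequate prophylaxis means, or point to where it is defined.
- State the highest exempt grade for the gastrointestinal, fatigue and electrolyte bullets, as the other five bullets do, and state that fatal events count.
- Reconcile Section 6.4.2 with Table 1 and with the Section 10.1 replacement rule, so that it is clear how a lead-in patient is handled when an exempt event ends sorafenib early.
- As a clarification only, state whether the thromboembolic bullet includes arterial events.

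The sponsor sets the clinical thresholds. The cost is a short wording amendment and a slightly higher chance of a lead-in hold. The boundaries in 13.6.2 and the sample size need not change.

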7 DOSE MODIFICATIONS

If the toxicity is not covered in [Table 1](#), [Table 2](#), [Table 3](#), or [Table 4](#), use the following general guidelines:

- Option to modify for grade ≥ 1 toxicity
- Recommendation to consider modification for grade ≥ 2 non-hematologic toxicity, other than PPE (see sorafenib dose-modification guidelines below)
- Requirement to modify for grade ≥ 3 non-hematologic toxicity
- Requirement to modify for grade 4 toxicity

Study treatment modification consists of dose omission and/or schedule adjustment of 1 or more agents as clinically appropriate and as described below. In general, agent(s) should be omitted pending resolution of toxicity to \leq grade 1 and then resumed at the same or a lower dose or frequency.

Should the occasion arise that one or more of the study agents need to be discontinued due to dose modification requirements, patients may continue on study at investigator discretion, taking single- or dual-agent study drug treatment, with the following exception: if both valproic acid and sorafenib must be permanently stopped, study treatment will be discontinued.

Patients are not required to be removed from study treatment for a qualifying toxicity (Section [6.4.2](#)). Removal from the study treatment for safety reasons may be considered at the treating physician's discretion, based on the severity/type of toxicity.

7.1 Sorafenib

Sorafenib dose reductions (to be followed decrementally in this order):

- 400 mg twice daily
- 400 mg daily
- 200 mg daily
- 200 mg twice daily dosed every other day
- If cannot tolerate lowest sorafenib dose, discontinue sorafenib

If toxicities leading to modification resolve to \leq grade 1, the sorafenib dose may be escalated in increments of 200 mg per day after cycle 1 but not beyond a patient's enrollment dose.

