7.1.1 Sorafenib Dose Modifications

Table 1. Sorafenib Dose Modifications

Toxicity		Sorafenib Modification
Cardiac		
Grade \geq 2 acute coronary syndrome (myocardial ischemia) or Grade \geq 2 myocardial infarction		Discontinue sorafenib permanently.
Heart failure	Grade 3	
 Interrupt until \leq grade 1; upon resumption, decrease by 1 dose level. If no recovery after 30 day interruption, discontinue sorafenib permanently unless patient is deriving clinical benefit; confer with PI.
	Grade 4	Discontinue sorafenib permanently.
Skin and Subcutaneous Disorders		
Palmar-plantar erythrodysesthesia syndrome (PPE) (hand-foot syndrome)		See Table 2 'Sorafenib Dose Reduction Guidelines for PPE (Hand-Foot Syndrome).'
Grade 2 rash acneiform		At investigator's discretion, consider holding and/or reducing sorafenib to the next lower dose.
Grade 3 or grade 4 rash acneiform		Hold sorafenib. 
 Re-evaluate at least weekly until resolution to \leq grade 1 or tolerable grade 2. Re-start sorafenib at one dose reduction. If toxicity persists > 14 days, discontinue sorafenib. Patients with grade 4 acneiform rash related to sorafenib may be taken off sorafenib at investigator's discretion.
Stevens-Johnson syndrome or toxic epidermal necrolysis		Discontinue sorafenib if Stevens-Johnson Syndrome or toxic epidermal necrolysis are suspected.
Gastrointestinal Disorders		
Perforation (esophageal, gastric, colonic, duodenal, ileal, jejunal, rectal, or small intestine)		Discontinue sorafenib permanently.

Investigations	

Grade \geq 3 ALT increase in the absence of another cause or
 
AST or ALT $>$3x ULN with bilirubin $>$2xULN in the absence of another cause; or
 
Grade \geq 1 Alkaline phosphatase in the absence of known bone pathology with grade \geq grade 2 bilirubin increase; or
 
any 1 of the following INR \geq 1.5, ascites and/or encephalopathy in the absence of underlying cirrhosis or other organ failure related to drug-induced liver injury
	
Discontinue sorafenib permanently.

Lab abnormalities - not clinically significant
 
Note: For clinically significant lab abnormalities follow the dose modification guidelines for "All Other Non-Hematologic Toxicities."
	
Continue sorafenib and institute supportive measures. At investigator's discretion, consider holding and/or reducing sorafenib to the next lower dose.

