Grade 3 electrocardiogram QT corrected interval prolonged	
See also Section 7.4.8
 
Hold sorafenib
 
 • Check and immediately administer potassium to achieve levels of ≥ 4 and magnesium to levels of ≥ 2. • Consider chronic oral supplementation of potassium and/or magnesium. • Review with principal investigator prior to patient's next scheduled treatment, considering the following options: 
 ○ STOP sorafenib until QTc recovers to pre-study treatment baseline (grade 1 or less, or ≤ 480ms). ○ When QTc returns to baseline, reinstitute sorafenib cautiously, with additional QTc monitoring at earliest possible follow-up opportunity, but no more than 8 days from reintroduction of sorafenib. ○ If QTc prolongation event felt attributable to sorafenib, reduce sorafenib to the next lower dose. • For recurrent QTc grade 3 felt attributable to sorafenib despite dose reduction, consider permanent discontinuation of sorafenib.
Grade 4 electrocardiogram QT corrected interval prolonged	Discontinue sorafenib. Do not restart.
Nervous System Disorders (potentially reflective of cardio-toxicity)	
Grade 2 pre-syncope or grade 3 syncope	
See also Section 7.4.8
 
 • Obtain ECG for cardiology review/consultation. • Check and immediately administer potassium to achieve level of ≥ 4 and magnesium to level ≥ 2. • If ECG shows new dysrhythmia or QTc \geq grade 2 (> 480ms), hospitalize for monitoring with Cardiology consultation. • STOP sorafenib until any potassium and magnesium abnormalities are corrected, symptoms resolved and QTc returns to grade 1 or less (≤ 480ms). • Reintroduce sorafenib cautiously, with input from Cardiology and with additional QTc evaluation, either concurrent with reintroduction or at earliest possible follow-up opportunity and no more than 8 days from reintroduction. • If event felt attributable to sorafenib, reduce sorafenib to the next lower dose. • Consider chronic oral supplementation of potassium and/or magnesium. • For recurrent syncope or near-syncope felt attributable to sorafenib, consider permanent discontinuation of sorafenib.
Vascular Disorders	
Hypertension	See Table 3 'Management of Hypertension.'
All Other Non-Hematologic Toxicities	
Grade ≥ 2 hemorrhage (requiring medical intervention)	Discontinue sorafenib permanently.

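### The last step of the sorafenib dose-reduction ladder (Section 7.1) leaves the average dose at 200 mg/day, so it changes the schedule without lowering the average dose

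*Combined protocol and SAP*

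**What the plan says.** Section 7.1 introduces its list with "Sorafenib dose reductions (to be followed decrementally in this order" and gives four rungs: 400 mg twice daily, 400 mg daily, 200 mg daily, and "200 mg twice daily dosed every other day". The list ends with "If cannot tolerate lowest sorafenib dose, discontinue sorafenib", so the fourth rung is presented as the lowest dose. Once toxicity has settled, "the sorafenib dose may be escalated in increments of 200 mg per day after cycle 1", up to the enrollment dose.

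The tables that follow use these rungs as dose levels:
- Table 1, grade 3 heart failure: "upon resumption, decrease by 1 dose level".
- Table 1, pre-syncope or syncope: "If event felt attributable to sorafenib, reduce sorafenib to the next lower dose".
- Table 1, grade 3 QTc prolongation: a step to the next lower dose appears in a list that the treating team reviews with the principal investigator, "considering the following options".
- Table 2, grade 2 hand-foot syndrome (PPE) that recurs: hold, then restart one level lower, with no limit on the number of recurrences.
- Table 3, symptomatic or persistent grade 2, or grade 3, hypertension: hold, then restart one step lower.

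The general text of Section 7 is broader. A modification may be an omission or a change of schedule, and an agent may be "resumed at the same or a lower dose or frequency".

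**The concern.** The ladder is meant to give less drug at each step. The wording of the fourth rung suggests a reduction, because dosing moves to alternate days, but it also moves from once to twice daily, and the two changes cancel. The last available response to recurrent toxicity before stopping sorafenib may then leave the amount of drug unchanged.

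At stake is whether a stated safety instruction does what it says. A clinician who steps a patient down from 200 mg daily because of heart failure, syncope or recurrent PPE would reasonably believe that the dose had been lowered. On average it has not.

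**Working it through.** **Inputs.** The four rungs come from Section 7.1. The 28-day cycle comes from Section 6.2. The plan states no average or cumulative dose for any rung, so there is no figure of its own to reproduce.

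**Formulas.** Average daily dose = (mg per intake × intakes per dosing day) ÷ days per dosing interval. Total per 28 days = mg per dosing day × number of dosing days.

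| Rung | Dosing days in 28 | mg per dosing day | Average mg/day | mg per 28 days | Change in average from rung above |
|---|---|---|---|---|---|
| 400 mg twice daily | 28 | 400 × 2 = 800 | 800 | 22,400 | – |
| 400 mg daily | 28 | 400 | 400 | 11,200 | 1 − 400/800 = 50% cut |
| 200 mg daily | 28 | 200 | 200 | 5,600 | 1 − 200/400 = 50% cut |
| 200 mg twice daily, alternate days | 14 | 200 × 2 = 400 | 400/2 = 200 | 400 × 14 = 5,600 | 1 − 200/200 = 0% |

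Each of the last two rungs gives 28 intakes of 200 mg per cycle (28 × 1 and 14 × 2). The single intake is unchanged, the number of dosing days halves, and the amount on a dosing day doubles.

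**In the protocol's own unit.** Re-escalation in Section 7.1 is expressed in mg per day. In that unit the rungs differ by 800 − 400 = 400, 400 − 200 = 200 and 200 − 200 = 0.

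**Comparison with sildenafil (Section 7.2).** That ladder runs 50 × 2 = 100, 25 × 2 = 50 and 25 × 1 = 25 mg/day. It falls at every step.

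**A path that reaches the last rung.** Grade 2 PPE under Table 2, without re-escalation in between:
- 1st episode: 800 to 400 mg/day.
- 2nd episode: 400 to 200 mg/day.
- 3rd episode: 200 to 200 mg/day.

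Grade 3 PPE alone does not get there, because Table 2 stops sorafenib at its third occurrence.

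**Table 1, other grade 3 non-hematologic toxicity.** This row calls for two reductions at the 2nd or 3rd occurrence and three at the 4th. It does not say where the count begins.
- Counted from the starting dose, two reductions give 200 mg/day and three also give 200 mg/day, so the response does not rise.
- Counted from the current dose, a patient on 400 mg daily after the 1st occurrence goes straight to the last rung at the 2nd, a real cut from 400 to 200 mg/day. On that reading the two equal rungs never meet in this row.

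**Candidate replacement.** 200 mg once every other day gives 200 × 14 = 2,800 mg per 28 days, or 100 mg/day, a further 50% cut.

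**The case against.** The strongest reply is that Section 7 counts a change of schedule as a modification and allows a lower dose or a lower frequency. Alternate-day dosing has fewer dosing days, and the protocol nowhere says that a lower dose means a lower average dose. It follows that the schedule is not prohibited and that no stated figure is wrong. This does not settle the matter. Section 7.1 calls the list dose reductions and its end the lowest dose, and the table rows ask specifically for a lower dose or dose level. No visible text redefines this rung.

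Other limits stand:
- The patient must already have had two reductions.
- Grade 4 toxicities that require stopping sorafenib, and holds until recovery, still apply.
- Recurrent syncope or QTc prolongation prompts consideration of permanent discontinuation.
- Section 7.1.3 prefers medical control of blood pressure to changing sorafenib.
- Section 1.7 allows sildenafil reductions if modifying sorafenib or valproic acid fails.
- Section 7.6 lets the investigator stop treatment in the patient's interest.

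A reader might infer that the last rung is more toxic, because 400 mg is taken on each dosing day, or that it is a slip for once-daily dosing. The documents support neither inference. The single intake stays at 200 mg, a drug-free day is added, and Section 9, to which the study calendar refers for sorafenib dosing, is blacked out. The sponsor's reason for the rung cannot be seen.

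**Conclusion.** The point holds in a narrow form. The last rung is labelled and used as a lower dose level, but its average dose equals that of the rung above it: 200 mg/day, a 0% step after two steps of 50%. This follows from the plain wording, two 200 mg intakes on alternate days, and needs no outside figure.

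It concerns only patients who reach a third reduction, for example through a third grade 2 PPE episode without re-escalation, or through grade 3 heart failure or sorafenib-attributed syncope while on 200 mg daily. The documents give no frequency for this. The observation about three reductions in Table 1 holds only if they are counted from the starting dose.

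A reader might also infer that the trial's safety monitoring is weakened. It is not: the lead-in and sequential rules in Section 13.6 count qualifying toxicities, which Section 10.1 restricts to the first cycle, and no threshold uses dose. What remains is a patient-management instruction that should be corrected.

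**What to change.** Replace the last rung in Section 7.1 with one that is lower, for example 200 mg once every other day (average 100 mg/day, 2,800 mg per 28 days). The documents do not support any particular level, so the sponsor should confirm it. The re-escalation sentence must change as well. Returning from 100 to 200 mg/day is a 100 mg/day step, which the present 200 mg/day increment does not provide for. It should say that re-escalation from the last rung goes to 200 mg daily.

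If the sponsor intends only a schedule change here, Section 7.1 should say so, and Tables 1 to 3 should not count the rung as a lower dose level. The text would then need to state what happens to a patient on 200 mg daily who must step down.

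The cost of the replacement is two short edits in Section 7.1 and a lower dose for the patients on that rung. Endpoint, sample size and stopping boundaries are unaffected.
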